10.4 Assessment and Recording of Adverse Events

The SI will carefully monitor each participant throughout the study for possible AEs. All AEs will be documented on CRFs designed specifically for this purpose. All AEs will be collected and reported in the EDC system and compiled into reports for monthly reviewing by the MM. The MM shall promptly review all information relevant to the safety of the investigational product, including all SAEs. Special attention will be paid to those that result in permanent discontinuation of the investigational product(s) being studied, whether serious or non-serious.

10.4.1 Assessment of Adverse Events

At each visit (including remote visits), the participant will be asked if they have had any problems or symptoms since their last visit in order to determine the occurrence of adverse events. If the participant reports an adverse event, site staff will probe further to determine:

1. Type of event
2. Date of onset and resolution (duration)
3. Severity (mild, moderate, severe)
4. Seriousness (does the event meet the above definition for an SAE)
5. Causality, relation to investigational product and disease
6. Action taken regarding investigational product
7. Outcome

If the infusion is done at home, confirmation of infusion and information on infusion-related adverse events, and changes in health and medications will be provided to study site by the home infusion nurse via study provided source documents. Site staff will then enter the data into the EDC system and follow up with the participant as needed to document any changes in AEs or concomitant medications in the EDC system.

10.4.2 Severity of Event

The following guidelines will be used to describe severity.

- **Mild** – Events require minimal or no treatment and do not interfere with the participant's daily activities.
- **Moderate** – Events result in a low level of inconvenience or concern with the therapeutic measures. Moderate events may cause some interference with functioning.

- **Severe** – Events interrupt a participant’s usual daily activity and may require systemic drug therapy or other treatment. Severe events are usually potentially life-threatening or incapacitating. Of note, the term “severe” does not necessarily equate to “serious”.

10.4.3 Relatedness of Adverse Event to Investigational Product

The relationship of the AE to the investigational product should be specified by the SI based on temporal relationship and his/her clinical judgment, using the following definitions:

- **Related** – The AE is known to occur with the study intervention, there is a reasonable possibility that the study intervention caused the AE, or there is a temporal relationship between the study intervention and event. Reasonable possibility means that there is evidence to suggest a causal relationship between the study intervention and the AE.
- **Not Related** – There is not a reasonable possibility that the administration of the study intervention caused the event, there is no temporal relationship between the study intervention and event onset, or an alternate etiology has been established.

10.4.4 Recording of Adverse Events

All clinical Adverse Events and Key Study Events (e.g., Mortality, Pregnancy, PAV, and Tracheostomy) are recorded in the participant’s study binder. The site should enter the AE and Key Study Event information into the EDC system as soon as possible after learning of the event or receiving an update on an existing event.

Entries on the AE Log (and into the EDC system) will include the following: description of the event, severity, seriousness, date of onset, date of resolution, relationship to investigational product, action taken, and primary outcome of event.

10.5 Adverse Events and Serious Adverse Events - Reportable Events

The following are considered reportable events and must be reported to the CC within 24 hours of the site being notified of the event: all events that meet the above criteria for SAEs.

The MM reviews AE reports, compiled by Data Management, as described in the safety monitoring plan. The MM will review data on enrollment, abnormal laboratory results and protocol deviations. These reports will collectively be known as the Medical Monitor Report. The MM communicates with the IND Holder / Sponsor, and the CC as needed for reporting of SAEs to the FDA within the required timeframe per FDA investigational new drug application (IND) regulations.

All AEs that meet the criteria for a serious, unexpected, suspected adverse drug reaction (SUSAR), for which there is a reasonable possibility that the investigational product caused the event, in the opinion of the IND Holder / Sponsor, will be submitted to FDA in an expedited fashion.

Death, respiratory failure, and hospitalization for routine procedures (i.e., g-tube placement) will not be reported individually in an expedited manner because they are anticipated to occur in the study population at some frequency independent of drug exposure.

10.6 Pregnancy

If, following the baseline visit, it is subsequently discovered that a participant is pregnant or may have been pregnant at the time of SLS-005 exposure, SLS-005 must be permanently discontinued. Protocol-required procedures for discontinuation and follow-up should be performed when possible.

Sites will instruct participants to contact the SI if they become pregnant while participating in this protocol. The SI must immediately notify the Medical Monitor of the event and complete the Pregnancy Form. Follow-up information regarding the course of the pregnancy, including perinatal and neonatal outcome and, where applicable offspring information must also be reported on a Pregnancy Report Form. Any pregnancy that occurs in a female partner of a male participant should be reported to the sponsor and Medical Monitor. Information on this pregnancy will be collected on the Pregnancy Report Form, as appropriate.

11.0 PRIVACY AND CONFIDENTIALITY

- Study procedures will be conducted in a private setting
- Only data and/or specimens necessary for the conduct of the study will be collected
- Data collected (paper and/or electronic) will be maintained in a secure location with appropriate protections such as password protection, encryption, physical security measures (locked files/areas)
- Specimens collected will be maintained in a secure location with appropriate protections (e.g. locked storage spaces, laboratory areas)
- Data and specimens will only be shared with individuals who are members of the IRB-approved research team or approved for sharing as described in this IRB protocol
- Data and/or specimens requiring transportation from one location or electronic space to another will be transported only in a secure manner (e.g. encrypted files, password protection, using chain-of-custody procedures, etc.)
- All electronic communication with participants will comply with Mass General Brigham secure communication policies (or local institutional secure communication policies)
- Identifiers will be coded or removed as soon as feasible and access to files linking identifiers with coded data or specimens will be limited to the minimal necessary members of the research team required to conduct the research
- All staff are trained on and will follow the Mass General Brigham policies and procedures (or local institutional policies and procedures) for maintaining appropriate confidentiality of research data and specimens
- The PI will ensure that all staff implement and follow any Research Information Service Office (RISO) requirements (or local institutional policies) for this research
- Additional privacy and/or confidentiality protections: Study participant medical information obtained by this study is confidential, and disclosure to third parties other than those noted below is prohibited. Upon the participant's permission, medical information may be given to his or her personal physician or other appropriate medical personnel responsible for his or her welfare. All local and federal guidelines and regulations regarding maintaining study participant confidentiality of data will be adhered to. Data generated by this study must be available for inspection by representatives of the US FDA, the Office for Human Research Protections (OHRP), the sponsor, all pertinent national and local health and regulatory authorities, the CC or their representative, Study Monitoring personnel, the central IRB, DSMB, Study Steering Committee personnel, study biostatistician group, and National Institutes of Health (NIH). Deidentified data generated by this study may be shared with other researchers for future medical research.

Appendix A: Dosing Chart

The following dosing chart provides the number of bags of study drug to be administered based off body weight to achieve a dose of 0.75 g/kg. Actual volume of study drug to be administered will be calculated based off of patient weight. Refer to Pharmacy Manual Appendix 4.

Number of IV Bags	Weight Range in Kilograms
1	≤ 36.2 kg
2	36.3 to 72.4 kg
3	72.5 to 108.6 kg
4	108.7 to 144.8 kg

Dose Calculation:

1. Calculate Participant weight in kg

_____ lbs/2.2 → _____ kg

2. Calculate dose (g) using weight from step 1

0.75g x _____ kg → _____ g

[figure not shown]
3. Calculate Volume (mL) using calculated dose from step 2

_____ g / 0.0905 → _____ mL

[figure not shown]
Total volume to infuse

Appendix B: ALSFRS-R

REDACTED - COPYRIGHT PROTECTED MATERIAL

REDACTED - COPYRIGHT PROTECTED MATERIAL

[figure not shown]

Mass General Brigham Institutional Review Board
Intervention/Interaction Detailed Protocol

[figure not shown]
Evaluator's Initials: _____

Appendix C: ALSAQ-40

[figure not shown]
REDACTED - COPYRIGHT
PROTECTED MATERIAL

[figure not shown]
**REDACTED - COPYRIGHT
PROTECTED MATERIAL**

[figure not shown]
REDACTED - COPYRIGHT
PROTECTED MATERIAL

[figure not shown]
REDACTED - COPYRIGHT
PROTECTED MATERIAL

[figure not shown]
**REDACTED - COPYRIGHT
PROTECTED MATERIAL**

REDACTED - COPYRIGHT
PROTECTED MATERIAL

[figure not shown]
**REDACTED - COPYRIGHT
PROTECTED MATERIAL**

**REDACTED - COPYRIGHT
PROTECTED MATERIAL**

**REDACTED - COPYRIGHT
PROTECTED MATERIAL**

Appendix D: Data Monitoring Committee / Data and Safety Monitoring Board

A Data Monitoring Committee (DMC) or Data and Safety Monitoring Board (DSMB) will be convened for safety monitoring of this research study. The following characteristics describe the DMC/DSMB convened for this study (Check all that apply):

- The DMC/DSMB is independent from the study team and study sponsor.
- A process has been implemented to ensure absence of conflicts of interest by DMC/DSMB members.
- The DMC/DSMB has the authority to intervene on study progress in the event of safety concerns, e.g., to suspend or terminate a study if new safety concerns have been identified or need to be investigated.
- Describe number and types of (i.e., qualifications of) members:
At least 3 members including statistician, endocrinologist, and neurologists
- Describe planned frequency of meetings:
Bi-annual
- DMC/DSMB reports with no findings (i.e., “continue without modifications”) will be submitted to the IRB at the time of Continuing Review.
- DMC/DSMB reports with findings/modifications required will be submitted promptly (within 5 business days/7 calendar days of becoming aware) to the IRB as an Other Event.

1.1	28 November 2024	Version 3.0, 31 July 2023	
1. Section 4.3: Add summary on end of treatment and duration of study.
 
2. Section 4.4.1: add baseline characteristics of Presence of NIV, Gastrointestinal tube insertion.
 
3. Section 4.9.1: add new exposure summary for participants with TEAE related to study rug.
 
4. Section 4.9.2: add new AE tables
 
5. Throughout this SAP document, the term 'historical placebo' is updated to 'historical control'. The chosen external Answer ALS database also contains participants with medications administered for ALS, and no specific field can be used to identify all the participants without medications, so it is agreed to use all available data from Answer ALS.
 
6. Section 4.1.1: add definition of Baseline and Day 1 for historical control group which has no first dose date collected and uses the date of first study visit as baseline time point.
 
7. Section 4.4.3: For balance diagnosis between Trehalose group and historical control group after PS matching and stratification: exclude the p-value which should be used with caution. It is sufficient to only present the standard mean difference which is the most commonly used statistic to examine the balance of covariate distribution between treatment groups.

1.1	08 January 2025	Version 3.0, 31 July 2023	
1. Section 4.7.1.2: For OS comparison analysis under PSM, the bulbar onset (yes/no) is excluded from the stratification factor since the PS matched ID is constructed based on the PS score which includes the variable of bulbar onset.
 
2. Section 4.7.3: For % predicted VC comparison between PS matched Trehalose and historical control group, more details about the model are added.

2.0	20 March 2025	Version 3.0, 31 July 2023	Finalized version 2.0.

TABLE OF CONTENTS

SAP VERSION HISTORY	4
LIST OF TABLES	7
LIST OF FIGURES	7
LIST OF ABBREVIATIONS	8
1. INTRODUCTION	10
1.1 Study Objectives and Endpoints	11
1.2 Study Design	12
2. STATISTICAL HYPOTHESES AND MULTIPLICITY ADJUSTMENT	13
3. ANALYSIS SETS	13
3.1 Definition of Analysis Sets	13
3.2 Violations and Deviations	13
4. STATISTICAL ANALYSIS	14
4.1 General Considerations	14
4.1.1 Definitions, Derivations and Classifications	14
4.1.2 Windowing, Unscheduled Visits and Repeat Test Results	15
4.1.3 Dropouts, Missing/Incomplete Data, and Outliers	16
4.2 Historical Controls	17
4.2.1 Eligible Historical Control Analysis Set	17
4.2.2 PS Estimation	17
4.2.3 PS Matching	18

ANCOVA	Analysis of Covariance
ATC	Anatomic Therapeutic Chemical
BMI	body mass index
C-SSRS	Columbia-Suicide Severity Rating Scale
CI	confidence interval
DSMB	Data Safety Monitoring Board
DPP	Data Presentation Plan
EAP	Expanded Access Protocol
eCRF	electronic case report form
FALS	Familial Amyotrophic Lateral Sclerosis
FAS	Full Analysis Set
FDA	Food and Drug Administration (US)
FVC	Forced Vital Capacity
HR	hazard ratio
ID	identifier
IV	intravenous
MedDRA	Medical Dictionary for Regulatory Activities
Nfl	neurofilament light
NIV	ventilation, noninvasive
OPMD	oculopharyngeal muscular dystrophy
OS	overall survival
PAV	permanent assisted ventilation
PMLE	penalized maximum likelihood estimation

LIST OF ABBREVIATIONS

Abbreviation	Description
PPS	Per-Protocol Set
PS	propensity score
PT	preferred term
Q1	lower quartile
Q3	upper quartile
SAE	serious adverse event
SALS	Sporadic Amyotrophic Lateral Sclerosis
SAP	Statistical Analysis Plan
SCA3	spinocerebellar ataxia type 3
SD	standard deviation
SE	standard error
SOC	system organ class
SOD	superoxide dismutase
SVC	Slow Vital Capacity
TEAE	treatment emergent adverse event
TFL	table, figure, listing
VC	Vital Capacity
WHODD	World Health Organization Drug Dictionary

1. INTRODUCTION

Amyotrophic lateral sclerosis (ALS) is a serious, life-threatening, rare degenerative disorder of large motor neurons of the cerebral cortex, brain stem and spinal cord that results in progressive wasting and paralysis of voluntary muscles [1]. The incidence of ALS is currently approximately 2/100,000/year [2,3] and may be increasing [4]. The lifetime ALS risk is 1 in 600 to 1 in 1000. Even though the incidence of ALS is similar to that of multiple sclerosis [5], the prevalence is only 4- 6/100,000 (about 25,000 participants in the United States), due to the higher mortality rate. Fifty percent of people with ALS die within three years of onset of symptoms and 90% die within five years [5]. The median age of onset is 55 years. The cause in most cases is unknown. Age and gender are the only risk factors repeatedly documented in epidemiological studies [6]. There is a slight male predominance (3:2 male to female ratio) in sporadic ALS.

No treatment prevents, halts or reverses the disease, although riluzole use is associated with a 10% prolongation of survival [7, 8], and edaravone, an antioxidant, slows illness by approximately 33% in some people [9]. The majority of people with ALS have sporadic (SALS) disease; 10% are familial (FALS). Natural history studies have determined that age at onset, site of onset, delay from first symptom to entering ALS clinic, and rate of change in respiratory function are significant covariates of survival [12,13,14,15].

Trehalose is a disaccharide that is well known for its protein-stabilizing properties [16,17] and its ability to activate autophagy [18]. This was the basis for human trials of intravenous (IV) trehalose in oculopharyngeal muscular dystrophy (OPMD) and spinocerebellar ataxia type 3 (SCA3 or Machado Joseph disease). Trehalose has been shown to penetrate both muscle and brain. In recent years it became clear that trehalose exposure results in the activation of cellular pathways that are relevant to its use as a potential treatment of ALS.

Trehalose is not absorbed well in the human gut because of trehalase enzymes in the brush border that cleave the molecule into two glucose molecules. Seelos Therapeutics has developed an IV formulation to circumvent the breakdown of trehalose in the gut.

The clinical safety profile of trehalose and the nonclinical toxicology data support the investigation of SLS-005 as a potential treatment of ALS. Weekly dosing of SLS-005 is the only regimen to be evaluated in clinical trials to date (participants with OPMD and SCA3) and will be used in this trial. Participants with either sporadic or familial ALS accumulate TDP43 and participants with the superoxide dismutase (SOD) mutation accumulate SOD aggregates and thus have the potential to benefit from treatment with SLS-005 through activation of autophagy.

The is an intermediate expanded access protocol (EAP) trial to provide access to the investigational product, SLS-005, to participants with ALS who are not eligible to participate in clinical trials. The results might be included in a regulatory submission.

This statistical analysis plan (SAP) describes the detailed procedures for the planned statistical analyses of the efficacy, safety, and biomarker data that are collected. The endpoints are defined, and the statistical methods used to analyze them are presented. Table shells for the planned tables, figures, and listings (TFL) are included in a separate document, entitled “Data Presentation Plan” (DPP).

This version of the SAP has been developed using protocol version 1.0, dated 31 July 2023. Changes from the statistical methodology planned in the protocol are described in Section 7.

1.1 Study Objectives and Endpoints

Table 1 Objectives and Endpoints

Objective	Endpoint
PRIMARY	
To provide access to the investigational product, SLS-005, to about seventy (70) participants with ALS who are not eligible to participate in clinical trials.	Not applicable
EXPLORATORY	
To assess the disease progression in a broad population.	Overall survival Changes in ALS Functional Rating Scale-Revised (ALSFRS-R) scores Changes in Slow Vital Capacity (SVC) Changes in Amyotrophic Lateral Sclerosis Assessment Questionnaire-40 (ALSAQ-40) score
BIOMARKER	
To assess the markers of neurodegeneration	Changes in levels of serum neurofilament light (NfL) chain protein
SAFETY	
To assess the long-term safety of SLS-005 in a broad population of participants diagnosed with ALS who are not eligible to participate in clinical trials.	The incidence of treatment-emergent adverse events (TEAEs), and assessments of vital signs, clinical laboratory tests, and Columbia-Suicide Severity Rating Scale (C-SSRS)

1.2 Study Design

This is an intermediate EAP trial to provide access to the investigational product, SLS-005, to participants with ALS who are not eligible to participate in clinical trials. Planned enrolment is approximately 70 people living with ALS at up to 25 sites in the US. Participants will receive weekly 60- or 90-minute IV infusions of trehalose, 90.5 mg/mL, at a dose of 0.75g/kg at the study center or at home. This is the same treatment dosage and dosing interval used in regimen E of the HEALEY ALS Platform Trial.

This EAP will enroll two cohorts of participants:

- Cohort 1: participants who do not qualify for any reasonably accessible ongoing clinical trials. This population represents a completely different participant population than that represented in the Platform Trial.
- Cohort 2: participants who have completed the Platform Trial Regimen E RCT and/or OLE and are not eligible for enrollment in another treatment regimen of the platform study. At the completion of their participation in the EAP, these participants may have been exposed to up to 76 weeks of IV trehalose – important long-term safety data.

Specifically, this EAP will capture safety, biomarker, and clinical efficacy data to augment the Phase 2/3 Platform Trial data of IV Trehalose.

Participants may be screened over and up to a 21-day period prior to treatment initiation. Participants who meet the inclusion criteria and none of the exclusionary criteria may be enrolled into the EAP. Participants may initiate treatment on the same day as the combined Screening/Baseline Visit, provided consent was obtained and all inclusion and exclusion criteria have been satisfied and eligibility has been confirmed by the investigator prior to treatment initiation.

Participants may receive up to 24 weeks of weekly infusions per protocol. There are up to 25 infusions over 24 weeks (first infusion occurs at the Screening/Baseline Visit). In addition to infusion visits, participants will have three scheduled in-clinic visits at Screening/Baseline, Week 3, and Week 24, and 1 phone call or telemedicine visits at Week 12 during the treatment period. The follow-up safety call will take place 28 +/- 7 days after the participant's last dose of the investigational medical product.

A Data and Safety Monitoring Board (DSMB) will be convened for safety monitoring of this research study. The DSMB Charter provides additional details.

Figure 1 below displays the study design for the study. Table 7 and Table 8 in Appendix 1 displays the schedule of assessments in the study for Cohort 1 and Cohort 2, respectively.

Figure 1 Study Diagram

2. STATISTICAL HYPOTHESES AND MULTIPLICITY ADJUSTMENT

No formal hypothesis testing will be conducted in this study. All analyses will be descriptive in nature. Any modeling that is performed will focus on parameter estimation. The Trehalose treated EAP participants will be compared to predicted placebo progression using historical controls, the p-values will be included to characterize associations and treatment effect but will mainly be used for the exploratory purpose and will not be adjusted for multiplicity.

3. ANALYSIS SETS

3.1 Definition of Analysis Sets

The following analysis sets are defined for this study:

Analysis Set	Definition
Screened Set	All participants who signed the informed consent form.
Full Analysis Set (FAS)	All participants who received at least one dose of Trehalose.
Per-Protocol Set (PPS)	
All participants included in FAS and who satisfy all the criteria below:
 
 - Did not have a major protocol deviation that affected the scientific integrity of the trial. - Received at least 85% and not more than 125% of the prescribed infusion volume up to the point of drug withdrawal/ last infusion. Data after drug withdrawal/ last infusion will not be included. 
The PPS will be finalized prior to the database closure.

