4.7.1 Overall Survival

4.7.1.1 Definition of Endpoint

The overall survival (OS) will be calculated in months, defined as the time from the date of first study treatment administration to the date of death due to any cause. Participants not known to have died at the time of the analysis will be censored on the date they were last known to be alive.

OS time (months) = (date of event/censored - date of first study treatment administration + 1) / 30.4375.

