4.7.1.2 Main Analytical Approach

OS will be summarized for both EAP study treatment groups and historical control groups based on the FAS.

The number and percentage of participants with event or censored will be presented by treatment group. The Kaplan-Meier estimates of the quartiles of the survival distribution along with corresponding 95% confidence intervals will be calculated. The survival rate (%) and 95% CI will be displayed for 2 months, 4 months, 6 months, 7 months, and 8 months.

To assess the differences in OS between PS matched (based on the pre-specified caliper width for main analysis) Trehalose group and historical control group: the hazard ratio (HR) and corresponding 95% confidence interval will be estimated using the Cox proportional-hazards model, stratified by PS matched ID. The two-sided log-rank test stratified by PS matched ID will be performed for generation of the two-sided p-value, which will be considered statistically significant if $p < 0.05$. The Kaplan-Meier plot for Trehalose and historical control groups will be presented.

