4.7.1.4 Supplementary Analyses

For OS (Including PAV), one additional comparison between PS stratification-based Trehalose group and historical control group under FAS will be provided. Besides, the following analyses will be performed for the participants in PPS, using the same approaches as described above.

- OS and OS (Including PAV) summary for EAP study by treatment cohort and overall
- OS and OS (Including PAV) comparison between PS matched (based on the pre-specified caliper width for main analysis) Trehalose group and historical control group. If the stratified analysis is invalid due to lack of event in some strata, the unstratified HR and 95% CI, as well as unstratified log-rank p-value will be provided
- OS and OS (Including PAV) comparison between PS stratification-based Trehalose group and historical control group

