4.9.1 Extent of Exposure

A summary on the participants' study drug dose modification types (dose initiation, drug interrupted, drug withdrawn) along with primary reasons for dosage change during the study will be provided with number and percentage of participants, and number of events by treatment cohort and overall for FAS.

The following study drug dose exposure variables will be derived and summarized descriptively by treatment cohorts and overall, for FAS and PPS, respectively.

- Number of infusions administered as continuous variable and by categories (1-5, 6-10, 11-15, 16-20, 21-25).
- Number of participants with any treatment infusion interruption, and number of infusion interruptions
- Treatment duration (weeks): defined as (date of last administration – date of first administration + 7) / 7.
- Total volume prescribed (mL): defined as sum of all volume prescribed for the treatment duration, including the missed scheduled infusion visits if any before participants' last infusion. For the missed infusion visits without volume prescribed collected in eCRF, the volume prescribed will be imputed using the last available volume prescribed carried forward from the prior visit.

- Total volume infused (mL): defined as sum of all volume infused for the treatment duration.
- Prescribed dose intensity (mL/week): defined as Total volume prescribed (mL) / Treatment duration (weeks).
- Actual dose intensity (mL/week): defined as Total volume infused (mL) / Treatment duration (weeks).
- Relative dose intensity (%): defined as 100 x (Actual dose intensity / Prescribed dose intensity)
The relative dose intensity (%) will be summarized as continuous variable and presented categorically (< 85%, 85% to 125%, > 125%).

In addition, the same study drug exposure analyses above will be performed for participants with TEAEs related to study drug. Only the infusion data prior to the onset of study drug related TEAEs will be included. Treatment duration (weeks) is defined as (date of last administration prior to the onset of TEAE related to study drug - date of first administration + 7)/7, other exposure variables will be calculated within this treatment duration period.

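### The per-protocol data cut at last infusion (SAP 3.1) conflicts with the survival rules used for the PPS survival comparisons and, applied as written, removes nearly all trehalose deaths but no control deaths

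*SAP*

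**What the plan says.** SAP 3.1 draws the PPS from the FAS, so it contains trehalose-treated participants only. Its second criterion requires 85% to 125% of the prescribed infusion volume up to drug withdrawal or last infusion, and closes with "Data after drug withdrawal/ last infusion will not be included". No endpoint is exempted.

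SAP 4.7.1.1 counts death from any cause and sets the censoring rule: "Participants not known to have died at the time of the analysis will be censored on the date they were last known to be alive". Table 4 (SAP 4.7.1.3) does the same with PAV added as an event. SAP 4.7.1.2 adds: "The survival rate (%) and 95% CI will be displayed for 2 months, 4 months, 6 months, 7 months, and 8 months".

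For survival, SAP 4.7.1.4 says "the following analyses will be performed for the participants in PPS, using the same approaches as described above". The list includes "OS and OS (Including PAV) comparison between PS matched (based on the pre-specified caliper width for main analysis) Trehalose group and historical control group" and "OS and OS (Including PAV) comparison between PS stratification-based Trehalose group and historical control group". For the matched comparison it allows an unstratified hazard ratio and log-rank test if some strata lack events.

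Historical controls start at their first study visit (SAP 4.1.1) and must have known mortality (SAP 4.2.1). No end-of-treatment date or matching cut is defined for them. SAP section 7 does not mention the point.

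**The concern.** For survival in the PPS there are two instructions. One stops the data at the last infusion; the other follows each person to death or last known alive. The SAP does not say which governs.

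The choice matters because death always comes after, or at the earliest on the day of, a person's last infusion. A cut there is tied to the outcome in the treated group and has no counterpart in the controls. A programmer who applied SAP 3.1 as written would compare a group with almost no possible events against one with its deaths intact. SAP 4.7.1.2 attaches a p<0.05 significance label to this test, and a PPS result is normally read as support for the FAS result.

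**Working it through.** The SAP gives no event count, hazard ratio or power for OS, so there is no planned figure to reproduce.

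**1. Follow-up left after the cut.** With the SAP's OS formula, a Week 24 infusion on Day 168 gives (168 + 1)/30.4375 = 5.55 months. At the +14-day window limit it gives (182 + 1)/30.4375 = 6.01 months. The 7- and 8-month trehalose rates cannot then be estimated.

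**2. Assumed mortality.** The documents give none for this population. The Protocol 1.1 figures (half dead by three years from onset, 90% by five) give 1 − exp(−(ln 2/3) × 168/365.25) = 10.1% and 1 − exp(−(ln 10/5) × 168/365.25) = 19.1% over 24 weeks. They run from symptom onset and are only a guide. I use 5%, 10.1% and 20%.

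**3. Matched comparison, no trehalose death kept.** Assume an inert drug, the same exponential hazard λ = −ln(1 − m)/168 per day in both groups, infusions every 7 days, and trehalose censoring at the last infusion. A pair is informative only if the control dies before the partner's cut; a later control death stays in the data but adds nothing to the pair-stratified test. The probability of an informative pair is

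p = Σ(k = 0 to 23) e^(−7kλ)(1 − e^(−7λ))(1 − e^(−7kλ)) + e^(−168λ)(1 − e^(−168λ))

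= 0.0487 / 0.0957 / 0.1792 for m = 5% / 10.1% / 20%.

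With no trehalose deaths, the stratified log-rank chi-square equals the number of informative pairs, a. Three give p = 0.083 and four give p = 0.046, so significance needs a ≥ 4. The share of trials significant in favour of trehalose is P(Binomial(n, p) ≥ 4):

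| Matched pairs | m = 5% | m = 10.1% | m = 20% |
|---|---|---|---|
| 20 | 0.015 | 0.118 | 0.493 |
| 30 | 0.056 | 0.322 | 0.811 |
| 50 | 0.226 | 0.717 | 0.986 |
| 70 | 0.446 | 0.912 | 0.999 |

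Seventy is a ceiling: every planned participant in the PPS and matched. Without the cut, simulation gives 0.03 or less in that direction. The hazard ratio in these cells is estimated at 0, with no finite Wald interval, whenever there is an informative pair.

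**4. Deaths within one day of an infusion kept.** SAP dates are whole days, and a death dated on an infusion day is not after it. Simulation with a one-day allowance and 50 pairs gives about 0.16 / 0.44 / 0.71 (repeat runs differ by about 0.01). A separate run with 50 pairs, 10% six-month mortality, no early discontinuation and 8 months of follow-up shows the mechanism:

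- Trehalose deaths fall from 6.41 to 0.68 per trial; control deaths stay at 6.63.
- Pairs with the trehalose death first against the control death first go from 6.00 : 6.20 to 0.65 : 4.45. The apparent hazard ratio is 0.65/4.45, about 0.15, when the truth is 1.

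**5. Unstratified fallback.** In the same set of runs (50 pairs, one-day allowance, six-month mortality 5% / 10% / 20%, two-sided rejection), the unstratified log-rank test rejects in 0.145 / 0.403 / 0.728 with the cut and 0.055 / 0.055 / 0.047 without it. The stratified test gives 0.143 / 0.399 / 0.666 with the cut. The fallback does not cure the problem.

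**6. OS (Including PAV).** PAV that starts while infusions continue precedes the last infusion and is kept, so this endpoint is less affected. How much less depends on how often infusions continue after PAV, which the documents do not say.

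**The case against.** The best reply is that the sentence was never meant for survival. It sits inside the infusion-volume criterion. SAP 4.9.1 uses the same 85% and 125% limits and totals prescribed volume "including the missed scheduled infusion visits if any before" the last infusion, so the sentence may only keep later missed infusions out of the ratio. SAP 4.7.1.4 carries over the last-known-alive rule, and asking for 7- and 8-month rates presupposes longer follow-up. Endpoint text would often be preferred to a trailing clause in an analysis-set definition.

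This makes full follow-up a plausible intention, but it does not settle the matter. The preceding sentence of the criterion already limits the ratio to the period up to withdrawal or last infusion, so on the volume reading the clause is redundant. Nothing in the SAP states that reading or gives 4.7.1 precedence.

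Two objections to the size do stand. The figures in step 3 assume that no trehalose death is kept; step 4 shows a clear reduction if a few are. The mortality guides also ignore eligibility: Protocol 4.1 requires a life expectancy of at least 6 months in Cohort 1, and Cohort 2 has already completed earlier treatment periods. At 5% mortality with 20 to 30 pairs the rate is 0.015 to 0.056, near or below the nominal 0.05.

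The effect would also be visible: "The number and percentage of participants with event or censored will be presented by treatment group".

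**Conclusion.** The conflict between SAP 3.1 and SAP 4.7.1 is real. If the cut is applied to survival as written, the direction of bias follows from logic: nearly all trehalose deaths go, no control death is cut, and the comparison leans toward trehalose whatever the drug does. The size depends on mortality, pair count and how infusion-day deaths are handled. With 50 pairs it runs from 0.16 to 0.99 across the assumptions above, and with few pairs and low mortality it is negligible as a false-positive rate.

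A reader might infer three stronger things that the documents do not support:

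- That the trial's survival result is biased. The FAS OS analyses carry no such cut, and the PPS analyses are supplementary within a plan that SAP section 2 calls descriptive and exploratory.
- That every trehalose death must vanish and the hazard ratio must be 0. A death dated on an infusion day survives the cut.
- That the sponsor intends to censor survival at last infusion. The text permits that reading but does not establish it.

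Severity is minor to moderate. It is worth correcting because a stated rule, followed literally, gives a wrong answer.

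**What to change.** Add to SAP 3.1: *The cut at drug withdrawal/last infusion does not apply to OS or OS (Including PAV); for these, PPS participants are followed to death, PAV or date last known alive as in 4.7.1.1 and Table 4.* If the sentence concerns only the infusion-volume ratio, reword it to say so.

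The cost is one sentence. No new data are needed, because vital status is already collected to the last patient's last visit (Protocol 6.6.10), and the FAS analyses do not change.
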